1.2. Protocol Synopsis

Sponsor: Mitsubishi Tanabe Pharma Corporation	Name of Medical Product: MP-513	Active Ingredient(s): Teneligliptin
Study Centre(s): Multi-centre study that will be conducted in approximately 35 sites in China		
Study Duration: 30 weeks (2 weeks screening, 2 weeks placebo run-in, 24 weeks treatment, 2 weeks follow-up) The study period is estimated to start from [REDACTED] to [REDACTED].		Study Phase: 3
Study Title: A phase 3 randomized, double-blind, placebo-controlled parallel group efficacy and safety monotherapy study of MP-513 in Chinese subjects with type 2 diabetes mellitus inadequately controlled with diet and exercise		
Study objectives: To evaluate the efficacy and safety of MP-513 compared with placebo in Chinese subjects with type 2 diabetes mellitus inadequately controlled with diet and exercise		
Methodology: Multi-centre, randomized, double-blind, placebo-controlled, parallel-group study		
Number of Subjects (Planned): 240 subjects (120 subjects to MP-513 and 120 subjects to placebo)		
Diagnosis and Inclusion Criteria: The subjects have to meet all of the following inclusion criteria: 
 1. A signed and dated informed consent form has been obtained from the subject, in accordance with International Conference on Harmonisation guidelines on Good Clinical Practice (ICH GCP), before any screening or study related procedures take place. 2. The subject is aged ≥ 18 years at signature of the informed consent form 3. Hospitalization status: outpatient 4. The subject has had a documented diagnosis of type 2 diabetes mellitus for at least 3 months at the screening visit (Day -28) 5. The subject is undergoing diet and exercise therapy, and diet and exercise regimen has not been changed for at least 8 consecutive weeks at the screening visit (Day -28). Subjects who cannot do exercise due to complication are not limited to this criteria. 6. The subject's glycosylated fraction of haemoglobin (HbA1c) is $\geq 7.0\%$ and $< 10.0\%$ at the screening visit (Day -28) and on Day -14. 7. The subject's fasting plasma glucose (FPG) is < 270 mg/dL (15 mmol/L) at the screening visit (Day -28) and on Day -14. 8. The subject is capable of giving informed consent, complying with the restrictions and requirements of the protocol and, in the opinion of the investigator, will be able to complete the study. 		

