6.9.1.1 General Considerations

All significance tests will be carried out at a 5%, 2-sided significance level. Statistical tests will be supported by presenting estimates and 95% confidence intervals for the respective treatment effects and differences between the treatment groups. These estimates, confidence intervals and p-value will be based on the respective statistical models used for the analysis.

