6.9.4 Determination of Sample Size

[REDACTED]

7. Study Report and Publication Policy

Any formal presentation or publication of data from this trial will be considered by the appropriate sponsor personnel. For multi-centre studies it is mandatory that the first publication is based on data from all centres, analysed as stipulated in the protocol. Investigators agree not to present data gathered from one centre or a small group of centres before the full publication. In any case, the Sponsor will review any publications/communications/abstracts for accuracy (thus avoiding potential discrepancies with submissions to health authorities), verify that proprietary, confidential information is not being inadvertently divulged, and provide any relevant supplementary information.

8 References

[1] EMA 2012

Guideline on clinical investigation of medicinal products in the treatment or prevention of diabetes mellitus 14 May 2012 CPMP/EWP/1080/00 Rev. 1 Committee for Medicinal Products for Human Use (CHMP)

[2] ADA 2014

Diagnosis and Classification of Diabetes Mellitus. Diabetes Mellitus, Volume 36, Supplement 1, January 2014, S81-90

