7.2 Adjustments for Covariates

The efficacy variable being analysed will be adjusted for its baseline value, as a covariate in the model.

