8.7.1 Analysis of Primary Efficacy Variable

8.7.1.1 Primary Analysis of Primary Efficacy Variable

The primary efficacy endpoint is to evaluate the change in HbA1c from baseline to Week 24 in the group receiving MP-513 compared with the group receiving placebo in Chinese subjects with type 2 diabetes mellitus inadequately controlled with diet and exercise. The reduction in HbA1c value indicates improvement.

The primary efficacy will be assessed by testing the null hypothesis that, there is no difference in the change in HbA1c from baseline to Week 24 in the group receiving MP-513 compared to the group receiving Placebo. In statistical notation the hypothesis is defined as follows:

Null Hypothesis $H_0: \mu_{MP-513} = \mu_{Placebo}$

Alternate Hypothesis $H_A: \mu_{MP-513} \neq \mu_{Placebo}$

Where μ_{MP-513} : Mean change in HbA1c from baseline at week 24 for MP-513

μ_{Placebo} : Mean change in HbA1c from baseline at week 24 for placebo

The missing HbA1c values at week 24 will be imputed using LOCF approach prior to analysis. The change in HbA1c from baseline to Week 24 (LOCF) will be analysed using analysis of covariance (ANCOVA) with treatment as a fixed effect and baseline value as a covariate in the model.

For the treatment effects and the difference between the treatment groups, the least square means from ANCOVA will be presented along with the corresponding SE and CI. The treatment difference in mean change from baseline will be computed using the model. The p-values for the test of significance, SE and CI of the mean difference will be presented.

The change in HbA1c from baseline for all the post baseline assessments visits, Week 12 (LOCF) and Week 24 (LOCF) will also be summarized as continuous variable using descriptive statistics.

The line graph for mean change in HbA1c from baseline to Week 24 and Week 24 (LOCF) will be presented. The 95% CIs will also be shown in the graph with error bar. The plots of Week 24 and Week 24 (LOCF) will not be connected.

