8.7.2 Analysis of Secondary Efficacy Variables

All analysis on secondary efficacy variables will be performed using FAS.

The secondary efficacy endpoint is to evaluate the change in FPG from baseline to week 24 of MP-513 compared to Placebo. The same statistical methodology as described for primary analysis on primary efficacy endpoint will be used.

The line graph for mean change in FPG from baseline to Week 24 and Week 24 (LOCF) will be presented. The 95% CIs will also be shown in the graph with error bar. The plots of Week 24 and Week 24 (LOCF) will not be connected.

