11 APPENDICES

11.1 APPENDIX 1: STATISTICAL ANALYSIS AND PROGRAMMING DETAILS

11.1.1 Analysis of Covariance

This test will be used for testing whether population means of response variable (e.g. change in HbA1c from baseline to week 24) are equal across levels of treatment (MP-513 and Placebo) after controlling for the effect of continuous covariate i.e. baseline value and fixed effects i.e. treatment. Following code can be used for fitting ANCOVA model:

```
proc mixed data=mydata(where=(visit='Week 24'));  
  class trt;  
  model change = base trt/solution ddfm=kr;  
  lsmeans trt/diff=CONTROL('placebo') cl;  
  Ods output LSMeans = lsm (keep=trt estimate);  
  Ods output Diffs = diff1sm;  
run;
```

Where,

- Response variable 'change' is the change from baseline to an endpoint visit
- trt is a categorical variable for treatment group (MP-513 or placebo)
- base is continuous baseline covariate
- Class statement specifies the classification variables.

- *diff=CONTROL* requests the differences with a control that, by default, is the first level of the specified LS-mean effect. Thus to specify which level is to be considered as control specify that in parentheses i.e. ('placebo'),
- Dataset '*lsm*' will contain the estimate for least square means (LS-means) for treatment groups under the variable 'estimate'.
- Dataset '*diff_lsm*' will contain estimate of difference of LS- means under variable 'estimate', standard error of LS -means difference under variable 'stderr', p value (using t test) for testing the significance of the difference between LS-means under variable 'probt' and the confidence limits for difference of LS-means under variable 'lower' and 'upper'.

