11.1.2 Mixed Effects Model for Repeated Measure Analysis

This test will be used for testing whether population means of response variable (e.g. change in HbA1c from baseline to week 24) are equal across levels of treatment (MP-513 and Placebo) after controlling for the effect of continuous covariate i.e. baseline value and fixed effects i.e. treatment, visit and interaction of treatment and visit. Following code can be used for MMRM analysis:

```
proc mixed data=mydata;
  class subid trt visit;
  model change = base trt visit trt*visit / solution ddfm=kr;
  repeated visit/ subject=subid type=un;
  lsmeans trt*visit/cl diff;
  ods output LSMeans = lsm(keep=trt visit estimate where=(trt='MP-513' and
    visit='Week 24'));
  ods output Diffs = diff_lsm(keep=trt visit _trt _visit estimate stderr
    probt lower upper where=(trt='MP-513' & _trt='Placebo'
    & visit='Week 24' & _visit='Week 24'));
```

run;

Where,

- Response variable 'change' is the change from baseline to different visits.
- Class statement specifies the classification variables.
- trt is a categorical variable for treatment group (MP-513 or placebo)
- base is continuous baseline covariate
- Ddfm=kr specifies 'Kenwardroger' method of computing denominator degree of freedom for the tests of fixed effects.
- Type= un specifies the within- subject variance covariance matrix as 'unstructured variance covariance matrix'.
- Dataset '*lsm*' will contain the estimate for least square means (LS-means) for treatment groups at week 24 under the variable 'estimate'.
- Dataset '*diff_lsm*' will contain estimate of difference of LS- means under variable 'estimate', standard error of LS-means difference under variable 'stderr', p value (using t test) for testing the significance of the difference between LS-means under variable 'probt' and the confidence limits for difference of LS-means under variables 'lower' and 'upper'.

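### The efficacy models are valid but adjust only for the outcome's own baseline; adding the other Day 1 glycaemic measure may narrow the interval slightly (optional improvement)

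*SAP*

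**What the plan says.** SAP 7.2 sets the rule for all efficacy variables: "The efficacy variable being analysed will be adjusted for its baseline value, as a covariate in the model". SAP 8.7.1.1 applies it to the primary endpoint as "analysis of covariance (ANCOVA) with treatment as a fixed effect and baseline value as a covariate in the model", and SAP 11.1.1 codes it as "model change = base trt/solution ddfm=kr". The supportive MMRM in SAP 11.1.2 uses "model change = base trt visit trt*visit / solution ddfm=kr", again with one baseline term. For FPG, SAP 8.7.2 says: "The same statistical methodology as described for primary analysis on primary efficacy endpoint will be used". Protocol 6.9.1.5 specifies the same models.

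The visit schedule (Protocol Table 2) has HbA1c and FPG at screening, Day -14 and Day 1, and Protocol 6.6.1 sends the Day 1 samples to the central laboratory. SAP 6.3 takes the most recent value before randomization as baseline. Protocol 6.4.2 and SAP 4.3 describe static blocked randomization and name no stratification factor. Baseline FPG is linked to the HbA1c outcome only as an exploratory subgroup factor (SAP 7.10).

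**The concern.** HbA1c reflects glycaemia over past weeks, and FPG the current level. Each could help predict the other's Week 24 value beyond what the outcome's own baseline already explains. If it does, a model that leaves it out has a larger residual variance than necessary, and so a wider confidence interval for the primary endpoint and the only secondary endpoint. With no stratification, the design does not control chance imbalance in baseline FPG either. The HbA1c model handles such imbalance only as far as baseline HbA1c tracks it.

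Precision is what is at stake. Under randomization the own-baseline analysis is unbiased and keeps its type I error. A second pre-specified baseline covariate would not change that.

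**Working it through.** **Inputs from the documents.** Planned size is "240 subjects (120 subjects to MP-513 and 120 subjects to placebo", allocated 1:1. On alpha, the protocol says: "All significance tests will be carried out at a 5%, 2-sided significance level". For scale only, Protocol section 4 quotes an SD of HbA1c change of 0.67 (Japanese monotherapy, Week 52) and a placebo-subtracted effect of -0.48% (20 mg added to metformin, Week 24). The power, effect and SD behind 240 are redacted, so the plan's own sample-size figure cannot be reproduced. That is not a gap in the plan.

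**Input that must be assumed.** r is the partial correlation of the other measure's baseline with the Week 24 outcome, given treatment and the outcome's own baseline. The range shown is 0 to 0.3.

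**Step 1: effect on the ANCOVA variance.** The extra covariate multiplies residual variance by (1 - r²). It costs one residual degree of freedom (237/236) and an allowance for chance imbalance (1 + 1/235 = 236/235). The combined factor is

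(1 - r²) × (237/236) × (236/235) = (1 - r²) × 1.0085.

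The unadjusted-for-FPG 95% half-width at SD 0.67 is 1.96 × 0.67 × √(2/120) = 0.1695. Multiplying by the square root of each variance factor gives:

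| Assumed r | Variance factor | Change in variance | SE factor | Half-width (HbA1c, % points) | Equivalent extra subjects on 240 |
|---|---|---|---|---|---|
| 0 | 1.0085 | +0.85% | 1.004 | 0.170 | -2 |
| 0.1 | 0.9984 | -0.2% | 0.999 | 0.169 | about 0 |
| 0.2 | 0.9682 | -3.2% | 0.984 | 0.167 | 8 |
| 0.3 | 0.9177 | -8.2% | 0.958 | 0.162 | 22 |

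The last column is 240 × (1/factor - 1). Break-even is where 1 - r² = 235/237, so r = √(2/237) = 0.092. Counting the degree of freedom alone gives +0.4%, -0.6%, -3.6% and -8.6%, with break-even at √(1/237) = 0.065. The conclusion is the same.

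**Step 2: r could be zero.** The two baselines are themselves correlated, so part of the second one's information is already in the first. Let a be the correlation between baselines, b that of the outcome with its own baseline, and c that with the other baseline. Then r = (c - ab)/√((1 - a²)(1 - b²)). Taking a = 0.6 and b = 0.5 as an assumption, the denominator is √(0.64 × 0.75) = 0.693:

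- c = 0.3: r = 0, no gain.
- c = 0.4: r = 0.14, r² = 2.1%.
- c = 0.5: r = 0.29, r² = 8.3%.

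**Step 3: chance imbalance.** The standardised between-arm difference in a baseline variable has SD √(2/120) = 0.129, so 1.96 SDs is 0.253. Uncorrected, an imbalance of that size in the part of FPG not explained by HbA1c would move the HbA1c estimate by about r × 0.67 × 0.253. This is 0.017, 0.034 and 0.051 percentage points at r = 0.1, 0.2 and 0.3. This benefit also vanishes if r is zero.

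**Step 4: power.** With 120 per arm, effect 0.48 and SD 0.67, power is 0.9998 before any change. If SD were 1.0 (an assumption), it would go from 0.961 to 0.962, 0.967 and 0.974 at r = 0.1, 0.2 and 0.3, leaving out the small-sample cost.

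The FPG ANCOVA obeys the same variance formula with its own unknown r. No figure was derived for the MMRM.

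**The case against.** The strongest reply is that nothing is broken. Protocol, SAP and code agree, no stratification factor is omitted, and one pre-specified covariate is a legitimate choice. The same argument could be made for C-peptide, BMI or duration of diabetes. All of this stands, and it is why the point is an improvement and not an error.

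A reader might infer that the planned analyses certainly lose precision. The documents do not show this: they give no correlation, and below r of about 0.09 the extra term does slightly more harm than good.

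A reader might also infer that power is at risk. That too is unsupported. The sample-size inputs are redacted. At SD 0.67, 90% power corresponds to a true difference of (1.96 + 1.28) × 0.67 × √(2/120) = 0.28, smaller than every placebo-subtracted effect the protocol quotes, including -0.30% for 5 mg.

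Nor is the SAP 7.10 list evidence of prognostic value. Subgroups ask whether the treatment effect varies, and that list concerns HbA1c only. It does mean that baseline FPG is not wholly disregarded.

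Finally, the primary model is fixed in Protocol 6.9.1.5, so changing it means a protocol amendment, with IEC approval under Protocol 2.1 and 2.4 and about 35 planned sites. That cost is real and weighs against a gain of this size, but it shows no statistical harm from the change.

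**Conclusion.** The point holds as an optional efficiency refinement. The planned own-baseline ANCOVA and MMRM are valid. They do not adjust for a second glycaemic baseline that is already collected, and so may give up a modest amount of precision. Under assumed r of 0 to 0.3, the ANCOVA treatment-effect variance would change by between +0.85% and -8%. At r = 0.2 and SD 0.67, the 95% half-width goes from 0.170 to 0.167 percentage points.

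These figures rest on the assumed r, on all 240 subjects being analysed, and on a raw Week 52 SD of change standing in for the residual SD at Week 24. If that raw SD applied here, adjusting for own baseline would make the residual SD no larger, so the absolute gain would be no larger either.

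Because Protocol 6.3.3 ties discontinuation to FPG, a reader might infer that adding baseline FPG would settle the missing-data question. It could make the MMRM's assumption about missing values more plausible, but the documents give nothing to measure this, and LOCF in the primary ANCOVA would be unaffected.

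**What to change.** Before unblinding, amend SAP 7.2, 8.7.1, 8.7.2 and 11.1, with a matching line in Protocol 6.9.1.5:

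- HbA1c ANCOVA and MMRM: add baseline FPG as a second continuous covariate (in the ANCOVA code, `base base_fpg trt`).
- FPG ANCOVA: add baseline HbA1c (`base base_hba1c trt`).
- Use the SAP 6.3 baseline for both. Each measure is scheduled three times before treatment, so few subjects should be lost.
- Keep the single-covariate models as sensitivity analyses, and update SAP 5.1, which currently declares no planned changes to the analysis.

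The statistical cost is one degree of freedom: about 0.4% in standard error (0.85% in variance, counting the imbalance allowance) if the covariate proves useless. The administrative cost is the SAP revision and protocol amendment. No new data or subjects are needed. If the sponsor prefers not to amend the primary model, the two-covariate ANCOVA and MMRM can be pre-specified as sensitivity analyses instead.

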7.3 Handling of Dropouts or Missing Data

Subjects who discontinue the study prior to or after the initiation of the study drug will not be replaced and available data of these subjects until the point of discontinuation will be summarized. The missing baseline assessment will not be imputed.

For categorical variables with missing values, a category documenting the frequency of missing values will be displayed in the summary tables.

The missing HbA1c and FPG value at week 12 or week 24 will be imputed using last observation carried forward (LOCF) approach. Baseline value will not be used to impute missing data. The missing data of Fasting insulin, C-peptide, Glucagon, HOMA-IR, HOMA- β and Body weight at week 24 will also be imputed using LOCF approach.

The supportive analysis for primary efficacy will be done using observed values.

There will be no imputation of missing values in database of safety data, however missing relationship between AE and study medication will be considered as related to treatment following worst case principle. Missing severity of an AE will be summarized as severe AE.

7.3.1 TEAE status when start date is unknown

The following rules will apply in cases where start date of an AE is unknown:

- If the AE onset date is unknown and the end date is after Day 1 or ongoing, then the AE will be considered a TEAE.
- If the AE onset date is unknown and the end date is before Day 1, then the AE will not be considered a TEAE.
- If both the start and end dates are unknown (or end date is ongoing), then the AE will be considered a TEAE, following the worst case principle.

The same rule will be applied in cases where start date of a hypoglycemic episode is unknown.

7.4 Interim Analyses and Data Monitoring

No interim analysis is planned for this study. However, an independent Event Adjudication Committee (EAC) will be set up to evaluate the cardiovascular events.

7.5 Independent Event Adjudication Committee (EAC)

The study will have an independent EAC to adjudicate the cardiovascular events. The cardiovascular events are defined as:

- Death
- Myocardial Infarction
- Hospitalisation for Unstable Angina
- Stroke & TIA (fatal & non-fatal)
- Urgent Revascularisation Procedures

- Hospitalisation for Heart Failure

The adjudicated cardiovascular events will be used for the safety analyses.

7.6 Multi-center Studies and Pooling of Centers

This study will be conducted at approximately 35 sites in China. Data from all sites will be pooled and pooled data will be used for summary tables and analyses.

7.7 Multiple Comparisons/Multiplicity

Not applicable for this study as there is no multiple comparison and no interim analysis is planned.

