6.9.1.5 Efficacy Parameters

(1) Primary efficacy endpoint

The primary efficacy endpoint is the change in HbA1c from baseline to Week 24.

Primary analysis: The change in HbA1c from baseline to Week 24 between treatment groups will be analysed using analysis of covariance (ANCOVA), with treatment as fixed effect and baseline value as a covariate. Missing values at Week 24 will be imputed using LOCF approach. Primary analysis on primary efficacy endpoint will be presented for FAS.

Supportive analysis:

The same statistical methodology as described for primary analysis will be performed for PPS.

The change in HbA1c from baseline to Week 24 between treatment groups will be analysed using mixed-effects model for repeated measures, with treatment, visit and interaction of treatment and visit as fixed effects and baseline value as a covariate. An unstructured covariance matrix will be used to model the covariance of within-patient scores. No imputation will be implemented for missing values. This analysis will be presented for FAS.

(2) Secondary efficacy endpoint

The secondary efficacy endpoints are the change in FPG from baseline to Week 24.

The same statistical methodology as described for primary analysis on primary efficacy endpoint will be used. Analyses on secondary efficacy endpoint will be presented for FAS.

(3) Other efficacy endpoints

The other efficacy endpoints are;

- Proportion of subjects who achieved HbA1c < 7.0% at Week 24
- Change in fasting insulin, C-peptide, and glucagon from baseline to Week 24
- Change in HOMA-IR and HOMA-β from baseline to Week 24
- Change in body weight from baseline to Week 24
- Change in body weight from baseline to Week 12

For the proportion of subjects who achieved HbA1c < 7.0% at Week 24, the comparison between treatments will be performed using logistic regression with treatment as fixed effect and baseline value as a covariate. The subjects who has HbA1c ≤ 7.0% at baseline will be excluded from the analysis.

For the others, the same statistical methodology as described for primary analysis on primary efficacy endpoint will be used. Analyses on other efficacy endpoint will be presented for FAS.

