7 STATISTICAL METHODS

7.1 General Methodology

All analyses will be performed after the database is locked and access has been removed from the database and the study treatment codes are unblinded.

All statistical tests will be two-sided with a significance level of $\alpha=0.05$, unless specified otherwise and will be performed using SAS® Version 9.2 or higher.

Statistical tests will be supported by presenting estimates and 95% confidence intervals (CI) for the respective treatment effects and differences between the treatment groups. These estimates, confidence intervals and p-value will be based on the respective statistical models used for the analysis.

Data will be summarized using descriptive statistics (number of non-missing values [n], mean, standard deviation [SD], median, minimum, and maximum) for continuous variables and using frequency counts and percentage for discrete variables.

For the purpose of display, the summary results will be rounded as follows:

- Min and Max: same number of decimals as the raw data.
- Mean and Median: one more decimal place than the raw data.
- SD/Standard Error (SE): one more decimal places than the raw data.
- Percentages will be displayed with one decimal precision. A zero count will not have the associated percentage presented on the table (i.e. no 0%).
- All p-values will be displayed with a leading zero except when the value is 1. All p-values will be displayed to four decimal places. If a p-value is less than 0.0001, then the value will be displayed as '<0.0001'. If a p-value is 1, then the value will be displayed as 1.0000. If the p-value cannot be calculated for any reason, the value listed will be 'NA'.
- CI: one more decimal place than the raw data.

For categorical variables with missing values, a category documenting the frequency of missing values will be displayed in the summary tables.

Subject listings of all data from the CRFs as well as any derived variables will be presented. Safety listings of clinical laboratory, vital signs and ECG will be presented by planned visit.

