8.7.3 Analysis of Other Efficacy Variables

All other efficacy endpoint will be analysed using FAS. The other efficacy endpoints are as follows:

- Proportion of subjects who achieved HbA1c < 7.0% at Week 24
- Change in fasting insulin, C-peptide, and glucagon from baseline to Week 24
- Change in HOMA-IR and HOMA-β from baseline to Week 24
- Change in body weight from baseline to Week 24
- Change in HbA1c and FPG from baseline to Week 12

Proportion of subjects who achieved HbA1c < 7.0% at Week 24 (LOCF):

For the proportion of subjects who achieved HbA1c < 7.0% at Week 24 (LOCF), the comparison between treatments will be performed using logistic regression with treatment as fixed effect and baseline HbA1c value as a covariate. The subjects who have HbA1c < 7.0% at baseline will be excluded from the analysis.

The odds ratio (OR) with 95% Wald CIs will be presented for between treatment groups comparison of responder rate (i.e. proportion of subjects who achieved HbA1c < 7.0% at Week 24). The Wald Chi-Square p-value for significance of treatment effect after controlling for baseline HbA1c will also be displayed.

For logistic regression analysis, the dichotomous response variable will be coded as '1' (for subjects who achieved HbA1c < 7.0% at Week 24) and '0' for subjects for whom HbA1c ≥ 7.0% at week 24.

The frequency count and percentage of subjects who achieved HbA1c < 7.0% at week 24 will also be summarized by treatment groups.

Other efficacy endpoints:

For the remaining other efficacy endpoints, namely;

- Change in fasting insulin, C-peptide, and glucagon from baseline to Week 24
- Change in HOMA-IR and HOMA-β from baseline to Week 24
- Change in body weight from baseline to Week 24
- Change in HbA1c and FPG from baseline to Week 12

The line graph for mean change in other efficacy endpoints from baseline to Week 24 and Week 24 (LOCF) will be presented. The 95% CIs will also be shown in the graph with error bar. The plots of Week 24 and Week 24 (LOCF) will not be connected.

The same statistical methodology as described for primary analysis on primary efficacy endpoint will be used.

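### SAP 7.7 sets multiplicity aside, so the standing of the FPG test, the only secondary endpoint, is left undefined

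*SAP*

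**What the plan says.** On multiplicity, SAP 7.7 has a single sentence: "Not applicable for this study as there is no multiple comparison and no interim analysis is planned".

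The rest of the plan sets up several tests:

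- **Level.** Protocol 6.9.1.1: "All significance tests will be carried out at a 5%, 2-sided significance level". SAP 7.1 agrees: "All statistical tests will be two-sided with a significance level of" 0.05, unless specified otherwise.
- **Primary.** Protocol 6.9.1.5: "The primary efficacy endpoint is the change in HbA1c from baseline to Week 24". SAP 8.7.1.1 states one formal null hypothesis, for this endpoint only, and makes a p-value part of the method: "The p-values for the test of significance, SE and CI of the mean difference will be presented".
- **Secondary.** Change in FPG to Week 24 is the only secondary endpoint. SAP 8.7.2: "The same statistical methodology as described for primary analysis on primary efficacy endpoint will be used". The test does not depend on the HbA1c result.
- **Other.** SAP 8.7.3 lists the proportion below 7.0% HbA1c, for which "The Wald Chi-Square p-value for significance of treatment effect after controlling for baseline HbA1c will also be displayed". It then applies the primary method to fasting insulin, C-peptide, glucagon, HOMA-IR, HOMA-β, body weight, and HbA1c and FPG at Week 12.
- **Subgroups.** SAP 7.10 already calls these exploratory.

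Neither document gives a testing order, a gate or an adjustment. Neither says that the p-values for the secondary and other endpoints are nominal.

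**The concern.** A trial with one primary endpoint needs no adjustment for that endpoint. But once the plan names a secondary endpoint and tests it for significance at the full 5%, a reader of the report must know what a significant result means. It could be a confirmatory finding that follows from the primary, or a descriptive p-value. SAP 7.7 does not say, because it treats the question as not arising.

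At stake is the standing of an FPG claim. As written, nothing prevents FPG from being presented as a positive result when HbA1c has failed, and that is where the error rate for the pair exceeds 5%. To a lesser degree, the silence also leaves open how any of the other p-values might later be presented. Wording fixed before unblinding settles both credibly; wording added afterwards does not.

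**Working it through.** **Step 1: count the tested endpoints (SAP 8.7.1 to 8.7.3).**

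| Tier | Endpoints | Number |
|---|---|---|
| Primary | HbA1c change, Week 24 | 1 |
| Secondary | FPG change, Week 24 | 1 |
| Other | responder rate 1; insulin, C-peptide, glucagon 3; HOMA-IR, HOMA-β 2; body weight 1; HbA1c and FPG at Week 12 2 | 9 |

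The total is 1 + 1 + 9 = 11. The Protocol synopsis gives the same list. Protocol 6.9.1.5 instead has body weight at Week 12 in place of HbA1c and FPG at Week 12, which makes 10; the two lists combined make 12. The conclusion is the same on any of these counts.

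**Step 2: reproduce the plan's own figure.** The only error rate stated is 5% two-sided per test. For the single primary test, 1 − 0.95 = 0.05. That figure is intact, whatever is done with the other endpoints.

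**Step 3: error rate for HbA1c and FPG as written.** Suppose both null hypotheses are true and each is tested at 5% without a gate.

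- If independent: 1 − 0.95² = 1 − 0.9025 = 0.0975.
- Upper bound under any dependence: 0.05 + 0.05 = 0.10.
- If correlated: the documents give no correlation, so a range is assumed. Simulating 500,000 pairs of normal test statistics, each rejected beyond ±1.96, gives:

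| Assumed correlation | Chance of at least one false positive |
|---|---|
| 0.3 | 9.5% |
| 0.5 | 9.1% |
| 0.7 | 8.4% |
| 0.9 | 7.0% |

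**Step 4: error rate for the pair under a fixed sequence.** FPG is tested only if HbA1c is significant, so with both nulls true a false positive requires HbA1c to be falsely significant first. The chance of at least one is therefore 5%, whatever the correlation. HbA1c is still tested at the full 5%, so its power is unchanged.

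**Step 5: the other configurations.** If HbA1c truly responds and FPG does not, the FPG test alone has a 5% error rate with or without the gate. If FPG responds and HbA1c does not, the only possible error is on HbA1c, again 5%. The excess in step 3 therefore arises only when both are null.

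**The case against.** The strongest defence is that SAP 7.7 is right in the sense its authors probably meant: two arms, one primary endpoint, one stated hypothesis pair and no interim analysis. A reader might infer that the sentence is simply false, or that the primary conclusion is at risk. The documents support neither. The sentence is incomplete about endpoints, and the primary test is at 5%.

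A reader might also multiply out every test: 1 − 0.95¹¹ = 43% for the eleven endpoints, and more once the 28 subgroup levels are added. Those figures do not measure a fault in this plan, for three reasons:

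- They assume independence among tests that are clearly dependent. The responder rate is the primary variable cut at 7.0%, both HOMA indices are computed from FPG and insulin, and HbA1c and FPG each appear at two visits. At an assumed common correlation of 0.5 the eleven-endpoint figure is 30%, and at 0.9 it is 13%.
- The nine endpoints are already ranked below primary and secondary, a tier where familywise control is not normally required.
- SAP 7.10 already labels the subgroups exploratory. One of the 28 levels, more than 28 alcohol units a week, should be empty under exclusion criterion 9.

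The gate would also rarely bind if the drug works as it did before. Take as assumptions the Week 24 effect of 0.48 for 20 mg in the phase 2b metformin study and an SD of 0.76, the largest reported for the 52-week Japanese studies (both Protocol section 4), with 120 per arm. The standard error is 0.76 × √(2/120) = 0.098, the ratio is 0.48/0.098 = 4.9, and primary power exceeds 99%. At an assumed SD of 1.0 it is about 96%. These inputs come from other settings, and the trial's own sample-size section is redacted.

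Finally, neither document states a formal FPG hypothesis, so a confirmatory FPG claim may not be intended.

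All of this narrows the point, but does not remove it. FPG is named as the secondary endpoint and tested for significance, and the plan does not say how that result is to be read.

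**Conclusion.** The point holds in limited form. SAP 7.7 leaves the FPG test without a defined standing and the other endpoints' p-values without a nominal label. With HbA1c and FPG both null, the chance of at least one false positive for the pair is 9.75% under independence and never above 10%, against 5% under a fixed sequence. The values of about 9% and 7% rest on assumed correlations of 0.5 and 0.9.

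The practical effect is small if the drug lowers HbA1c as in earlier studies. The gain is then mainly clarity about what may be claimed. It is worth correcting before database lock because the remedy costs almost nothing.

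**What to change.** Replace the text of SAP 7.7 with:

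> Familywise error for the primary and secondary endpoints is controlled at 5% two-sided by a fixed sequence: HbA1c change at Week 24, then FPG change at Week 24 only if HbA1c is significant. P-values for all other efficacy endpoints are nominal; subgroup analyses remain exploratory (SAP 7.10).

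If the sponsor intends no claim on FPG, one sentence stating that its p-value is nominal would close the gap equally well.

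The cost is SAP wording only. Both tests stay at the two-sided 5% level set in Protocol 6.9.1.1, and neither sample size nor primary power changes. The downside is that FPG cannot be claimed if HbA1c fails. The change should be made before database lock, by when Protocol 6.9.1 expects the SAP to hold the full details.
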